**PROBIOTICS AND BREASTMILK ARE
ASSOCIATED WITH A DECREASED RISK OF
ATOPIC DERMATITIS IN VERY LOW BIRTH
WEIGHT PREMATURE INFANTS**

Study protocol and statistical analysis.
August 9, 2023.

STUDY PROTOCOL

BACKGROUND

Prematurity is associated with significant morbidity and mortality, including the prevalence of sepsis and gastrointestinal problems such as necrotising enterocolitis (NEC), among others. The aetiology is mainly due to immaturity, although numerous external factors play a role in aggravating its complexity. Some of these causes are increased gastrointestinal permeability, immaturity of the immune system, delayed colonisation and/or abnormal colonisation (dysbiosis), use of antimicrobials (sometimes prolonged), physiological limitation of the initiation of enteral nutrition... Some prenatal factors such as premature rupture of membranes or chorioamnionitis may also play a role, exposing them very early to pathogenic micro-organisms. These factors justify the higher risk of gut microbiota disruptions present in preterm infants compared to term infants.

The human microbiota plays a fundamental role in the development and maturation of the immune system. The symbiosis between microbiota and humans is essential in both innate and acquired immune maturation, intervening in the maturation of T cells and natural killer cells, proper regulation of the Th1-Th2 response, as well as in the tolerance of intestinal endotoxins.

Intestinal dysbiosis is conditioned by nutrition and healthy habits. In neonates, the main determinant of gut flora composition is diet and antibiotic exposure. Breast milk is the paradigm in neonatal nutrition, its microbiological content and macromolecules such as oligosaccharides in breast milk promote the growth of *Bifidobacterium* spp.

The use of probiotics in preterm infants, a population exposed to unfavourable environmental factors, may favour a more physiological development of the microbiota.

Numerous studies show that the use of probiotics in this population during the neonatal period reduces the development of NEC and late-onset sepsis in the short term. However, they also report other long-term beneficial effects on inflammatory, metabolic, neurological and gastrointestinal diseases, such as the reduction of allergic diseases throughout life, which is the focus of this study.

In recent decades, a significant increase in atopic-based diseases has been observed, in the pathophysiology of which metabolic activity triggered by gut dysbiosis seems to play a major role, as it has been observed that it may precede the onset of atopic dermatitis.

Atopic dermatitis is a chronic recurrent inflammation of the skin that leads to increased permeability, and therefore a loss of the skin barrier and increased risk of allergic sensitisation.

Several studies show the benefits of daily oral probiotics in the clinical improvement of atopic dermatitis and other atopic-based diseases with chronic inflammation, due to their effect on the development of immune tolerance. In the case of atopic dermatitis, a significant reduction in symptomatology and severity has been observed, as well as a reduction in the use of topical corticosteroids.

Factors involved in the early maturation of the immune system will condition the long-term development of atopic dermatitis. The use of oral probiotics composed of *Lactobacillus* spp. and *Bifidobacterium* spp. in the neonatal period may be a promising strategy against the development of atopic dermatitis due to their collaboration in the maturation and regulation of the immune system.

However, there is a lack of uniformity in the literature regarding the type of strains of choice, applicability of probiotics as prophylaxis or treatment, and in some of them even notable differences in results.

DESCRIPTION

In recent years there has been an increase in allergic diseases, which can be explained pathophysiologically by a dysregulation of the immune system. There are several lines of research into the cause of this increase, the best known of which is the "hygiene theory". Most agree that it could be due to a lack of immunological tolerance from a very early age.

The gut microbiota is directly involved in mediating immune tolerance to all antigens, including pathogenic and commensal mycobacteria, exposed at the level of the intestinal lumen. Currently, the use of probiotics is very popular in multiple diseases of an immunological and inflammatory nature, due to their interaction and modification of the microbiota, and therefore, with the immune system.

In neonatology, the use of probiotics is becoming increasingly widespread as a preventive measure against necrotising enterocolitis and late-onset sepsis. Based on theories about the interaction of probiotics with the immune system, it may be that the use of probiotics in this population may offer other medium- to long-term benefits in inflammatory diseases.

OBJETIVES

The main objectives are as follows:

1. To evaluate the association between nutritional factors in the neonatal period and atopic dermatitis, in relation to prevention.
2. To assess whether the use of breastfeeding and probiotic supplementation in very low birth weight infants as prophylaxis for necrotising enterocolitis is associated with a decrease in atopic dermatitis at preschool and school age.
3. To determine probiotic strains that offer benefits in reducing the occurrence of atopic disease.

The secondary objectives are set out below:

1. To assess whether the use of breast milk (both fresh and donated) offers a synergistic effect, when combined with probiotics, in the reduction of atopic dermatitis.
2. Impact of caloric and protein intake in very low birth weight infants on the development of atopic dermatitis later in life.

DESIGN AND METHODS

Observational retrospective cohort study in very low birth weight infants, <1500 grams and/or < 32 weeks, hospitalised in the Neonatal Intensive Care Unit at the Hospital Universitario Clínico San Cecilio between January 2009 and December 2021.

Enteral and parenteral nutritional data, type of feeding (fresh and/or thawed breast milk, donated breast milk or formula), probiotic administration and strain administered are recorded. Parental permission is available for all patients included in the study.

Inclusion and exclusion criteria:

All patients hospitalised in the Neonatal Intensive Care Unit with < 1500 grams birth weight and/or < 32 weeks at birth during the indicated time period. Deceased patients, incomplete or unavailable medical history and patients with severe congenital diseases are excluded.

Nutritional management:

The unit's nutrition and fluid management protocol, both enteral and parenteral, follows the recommendations of the Nutrition and Metabolism Group of the Spanish Society of Neonatology. Daily fluid (ml/kg/day), carbohydrate (mg/kg/min), protein (g/kg/day), lipid (g/kg/day) and calorie (kcal/day) intakes are calculated.

Given the characteristics of this group of patients, as described above, nutritional needs are often met with parenteral nutrition combined or not with enteral feeding. The objective is to cover the minimum needs to guarantee adequate growth and development of the newborn.

In relation to enteral nutrition, the first choice is fresh breast milk, sometimes it is necessary to freeze it for preservation, and it is thawed prior to use. In cases of unavailability, with parental consent, donated milk that has been pasteurised according to Holder's method is administered, or failing that, formula for premature infants.

Fortification with maternal or donated milk is started from one week of life, once water intake of at least 80 ml/kg/day has been achieved.

In our unit, the use of probiotics was initiated in December 2013 as a preventive measure against the development of necrotising enterocolitis. Two strains were available: *Lactobacillus Rhamnosus GG* and the combination of *Lactobacillus acidophilus* + *Lactobacillus bifidum*. The choice of the type administered depended on the preference of the responsible paediatrician. The probiotic was introduced after initiation of satisfactory enteral nutrition and continued until 35 weeks postnatal or until discharge from the unit.

Atopy registry:

Atopy is a state of abnormal hypersensitivity to exposure or contact with non-pathogenic antigens. We record a history of atopic dermatitis and first-degree family history.

STATISTICAL CONSIDERATIONS

In our study we have two types of descriptive variables: continuous variables and categorical variables.

- For continuous variables we will use the median and interquartile range, using the Mann-Whitney test for comparison.
- For categorical variables, distribution frequencies will be used, analysing them by means of Chi-square.

In order to study more than one variable on the desired effect, multivariate logistic regression analysis will be used.

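### Three overlapping main objectives name no primary contrast, and the plan does not say whether the crude tests or the logistic model supports the conclusion

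*Combined protocol and SAP*

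**What the plan says.** The Objectives section lists three main objectives of equal standing.

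- Main objective 1: "To evaluate the association between nutritional factors in the neonatal period and atopic dermatitis, in relation to prevention".
- Main objective 2: "To assess whether the use of breastfeeding and probiotic supplementation in very low birth weight infants as prophylaxis for necrotising enterocolitis is associated with" less atopic dermatitis in later childhood.
- Main objective 3: "To determine probiotic strains that offer benefits in reducing the occurrence of atopic disease".

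The first secondary objective asks about synergy between breast milk and probiotics. The second is "Impact of caloric and protein intake in very low birth weight infants on the development of atopic dermatitis later in life".

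Design and Methods lists the data collected: "type of feeding (fresh and/or thawed breast milk, donated breast milk or formula), probiotic administration and strain administered are recorded". Under Nutritional management it adds: "Daily fluid (ml/kg/day), carbohydrate (mg/kg/min), protein (g/kg/day), lipid (g/kg/day) and calorie (kcal/day) intakes are calculated".

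Statistical Considerations gives Mann-Whitney for continuous variables and, for the others, "For categorical variables, distribution frequencies will be used, analysing them by means of Chi-square". One further sentence says that multivariate logistic regression will be used to examine several variables together. The section states no significance level, multiplicity rule, covariate list or variable-selection rule, and does not say which analysis supports the conclusion. The title describes probiotics and breast milk as "ASSOCIATED WITH A DECREASED RISK OF" atopic dermatitis.

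**The concern.** The same exposure can appear under two objectives of different rank. Calories and protein are nutritional factors (main objective 1) and also form secondary objective 2. Breast milk belongs to main objectives 1 and 2. The preparations in main objective 3 subdivide the probiotic exposure in main objective 2. With no contrast named as primary, whichever exposure gives the most striking result can be presented as a main finding, and a reader cannot tell how many others were examined.

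The second gap is more serious. If the crude and adjusted results for an exposure disagree, the plan does not say which one counts. In a non-randomised cohort whose exposure is tied to calendar period, that leaves room for a confounded crude difference to become the headline.

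**Working it through.** The plan states no sample size, power, event count or significance level, so there is no figure of its own to reproduce. A two-sided 5% level is assumed throughout.

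**1. Are the crude comparisons confounded on the documents' own facts?**

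- Cohort window (Design and Methods): January 2009 to December 2021, which is 13 × 12 = 156 months.
- Probiotics started in December 2013 (Nutritional management). Months before that: 4 × 12 + 11 = 59.
- 59 / 156 = 37.8% of the window contains only unexposed infants.
- If outcomes were read at the protocol date of 9 August 2023 (an assumption; no date is given), children born before the start would be about 9.7 to 14.6 years old and those born after it about 1.6 to 9.7. Exposed children would then have had less time to acquire a recorded history of atopic dermatitis. That can favour probiotics, and a Chi-square test cannot separate it out.
- The preparation followed paediatrician preference, and probiotics began only once enteral feeding was established (Nutritional management).

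**2. How many exposure tests are implied?**

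- Named in the objectives: milk, probiotic yes/no, one overall preparation test, synergy, calories, protein = 6. The last three come from the secondary objectives.
- Recorded exposures for the main objectives, narrow: 5 intakes + 1 overall feeding test + 1 any-breast-milk contrast + 1 probiotic + 1 overall preparation test = 9.
- Recorded exposures, wide: 5 intakes + 4 feeding indicators + 1 any-breast-milk contrast + 1 probiotic + 3 preparation contrasts = 14. Adding 5 if enteral and parenteral intakes are tested separately gives 19.

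**3. Chance of at least one false positive**

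For k independent tests with no true effect, either direction: 1 − 0.95^k. Favourable direction only: 1 − 0.975^k.

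| k | Either direction | Favourable only |
|---|---|---|
| 6 | 26.5% | 14.1% |
| 9 | 37.0% | 20.4% |
| 10 | 40.1% | 22.4% |
| 15 | 53.7% | 31.6% |
| 19 | 62.3% | 38.2% |

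Independence cannot hold: calories derive from the macronutrients, and the preparation contrasts are nested within probiotic yes/no. Simulating equally correlated normal test statistics (200,000 replicates, either direction) gives:

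| k | ρ = 0.3 | ρ = 0.5 | ρ = 0.7 |
|---|---|---|---|
| 10 | 35.0% | 28.7% | 21.2% |
| 15 | 45.8% | 36.1% | 25.6% |

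These figures count each exposure once. Reporting both a crude and an adjusted version of each would add further opportunities.

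**The case against.** The strongest reply is that this is a retrospective observational cohort with essentially one outcome, that main objectives 1 and 2 speak only of association, and that a multivariate model is planned. Strict familywise control in such a study is partly a matter of preference. That stands, and so does the point that the choice among the exposures in main objective 2 belongs to the sponsor. But the plan never calls itself exploratory, main objective 3 sets out to identify beneficial strains, and the role and content of the model are undefined.

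Several stronger readings are tempting and are not supported:

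- A reader might infer that the plan commits to ten or more tests. It does not. The five intakes are said to be calculated, not tested, and only calories and protein are named in an objective.
- A reader might take 40% to 54% (10 to 15 tests) as the study's error rate. Those values need independence, which fails here.
- A reader might infer that every exposure is tested both crudely and in the model, or that a crude p below 0.05 would fulfil a main objective. The plan does not say which exposures enter the model and sets no success threshold. It introduces its variables as descriptive, so a descriptive role for the crude tests is plausible, though not stated.
- A reader might infer from the title that the data had already been analysed. The documents do not say.

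**Conclusion.** The concern holds as a gap in hierarchy, not as missing adjustment. The main objectives overlap one another and secondary objective 2, no contrast is primary, and the deciding analysis is unnamed. The confounding half carries more weight because it rests on stated facts: no exposed infants in 38% of the window, and preparation chosen by preference.

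The multiplicity half is real but its size is uncertain: about 26% (6 tests) to 54% (15 tests) under independence, and roughly 21% to 46% for 10 to 15 tests with correlation 0.3 to 0.7. These figures rest on an assumed 5% level and on counts that the plan does not give. The correction should be made, but it does not invalidate the study.

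**What to change.** 1. State that the adjusted odds ratio with 95% CI from the logistic model is the sole basis for the main conclusion, and that Chi-square and Mann-Whitney are descriptive. List the covariates: birth year or age at ascertainment, gestational age or birth weight, and family history of atopy. Naming the adjusted estimate without its covariates would not deal with confounding. Also tabulate probiotic use by birth year: if few infants went without it after December 2013, the model cannot separate exposure from calendar period, and the report should say so.
2. Name the primary contrast or contrasts from main objective 2, for example probiotic yes/no alone, or probiotic and breast milk as two co-primaries with Holm. Use one procedure, either a fixed sequence or Holm, not both.
3. Label the other nutritional factors, preparation comparisons, synergy, and calorie and protein intake exploratory: estimate and CI, no significance claim. Remove the duplication between main objective 1 and secondary objective 2.
4. If the data had already been examined when this hierarchy is set, report it as post hoc; it then gives little error protection.
5. Give the protocol a neutral title.

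The cost is wording. Family history is already recorded, and birth weight and gestational age define eligibility. The downside is that some nominally significant intake or preparation results could be reported only as exploratory.

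### Probiotics began part-way through the cohort, in December 2013, and the plan does not commit to separating probiotic use from birth era

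*Combined protocol and SAP*

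**What the plan says.** Design and methods describes a retrospective cohort from one neonatal unit, covering "between January 2009 and December 2021", with no restriction to the years when probiotics were in use. Nutritional management then says: "In our unit, the use of probiotics was initiated in December 2013 as a preventive measure against the development of necrotising enterocolitis". Which of two products an infant received depended on the paediatrician, and the product was started once enteral feeding was going well. The share of later infants who received one is not given.

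Main objective 2 asks whether breastfeeding and probiotic supplementation "is associated with a decrease in atopic dermatitis at preschool and school age". Secondary objective 1 asks whether breast milk "offers a synergistic effect, when combined with probiotics, in the reduction of atopic dermatitis". Main objective 3 asks which strains reduce atopic disease.

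Statistical considerations opens with "In our study we have two types of descriptive variables: continuous variables and categorical variables", and under that heading adds "For categorical variables, distribution frequencies will be used, analysing them by means of Chi-square". The only adjusted analysis is this: "In order to study more than one variable on the desired effect, multivariate logistic regression analysis will be used". No covariate is named, and the plan does not say whether the test or the model carries the conclusion. Atopy registry records a history of atopic dermatitis and first-degree family history, but fixes no age at which the outcome is counted.

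**The concern.** In most retrospective cohorts the link between a candidate confounder and exposure has to be argued. Here the plan's own dates establish it: before December 2013 nobody could be exposed, apart from infants still in the unit at the changeover. Anything else that differed between the eras and affects recorded atopic dermatitis will therefore show up in the probiotic-versus-none contrast unless the analysis deals with it.

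Two such influences can be read from the documents, and they pull in opposite directions. The Background reports that atopic disease has increased over recent decades. If that holds in this population, later (more often exposed) infants start from a higher risk and a benefit would be hidden. Against this, with no fixed age at ascertainment, later births have had less time to receive a diagnosis, which would look like a benefit.

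Main objective 2 and the synergy objective are affected. So is main objective 3 if it means each strain against none. Strain against strain is less affected only if both products were used over the same years, which is not stated. The calorie and protein objective is not defined by the 2013 start.

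**Working it through.** The plan gives no sample size, event rate or effect size, so there is no figure of its own to reproduce.

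**Inputs from the documents.** Window January 2009 to December 2021: 13 × 12 = 156 months (4,748 days). Start December 2013: 4 × 12 + 11 = 59 months earlier (1,795 days). Document date 9 August 2023.

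**Assumptions (not in the documents).** Even births; no probiotic effect; constant uptake u of 50% to 100% from December 2013; background risk changing by a constant proportion g per year.

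**Step 1: split by era.** p = 59/156 = 1,795/4,748 = 0.378 before probiotics; 1 − p = 0.622 after.

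**Step 2: how historical the comparator is.** Early share of the unexposed = p / [p + (1 − p)(1 − u)]. Concurrent unexposed infants, as a share of the cohort = (1 − p)(1 − u).

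**Step 3: spurious risk ratio.** This is the mean of (1 + g)^t over exposed birth dates divided by its mean over unexposed birth dates, with t in years from January 2009. Over an interval from a to b the mean is [(1 + g)^b − (1 + g)^a] / [ln(1 + g)(b − a)]. Example with g = +5% and u = 100%: the later era (4.91 to 13.00 years) averages 1.558 and the earlier era 1.130, so the ratio is 1.38. With u = 50% the unexposed average is 0.549 × 1.130 + 0.451 × 1.558 = 1.323, and 1.558/1.323 = 1.18.

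| Uptake u | Early share of unexposed | Concurrent unexposed | RR, +1% / −1% per year | RR, +5% / −5% per year |
|---|---|---|---|---|
| 50% | 55% | 31% | 1.04 / 0.96 | 1.18 / 0.82 |
| 70% | 67% | 19% | 1.04 / 0.96 | 1.23 / 0.79 |
| 90% | 86% | 6% | 1.06 / 0.95 | 1.31 / 0.75 |
| 100% | 100% | 0% | 1.07 / 0.94 | 1.38 / 0.72 |

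**Step 4: odds-ratio scale, as the logistic model would report.** If risk were 15% in the early era and 20% in the later one, with no probiotic effect, the odds ratio would be 1.42, 1.29 or 1.20 at 100%, 80% or 50% uptake. With the two risks exchanged it would be 0.71, 0.76 or 0.82.

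**Step 5: follow-up time.** At the document date (taken as the latest possible follow-up, an assumption), pre-probiotic births are 9.7 to 14.6 years old (mean 12.1) and later births 1.6 to 9.7 (mean 5.6). With a constant hazard h, risk is the mean of 1 − exp(−h × age). At h = 0.02 per year the risks are 0.215 (early) and 0.106 (later), giving an odds ratio of (0.106/0.894)/(0.215/0.785) = 0.43 at full uptake. For h from 0.01 to 0.04 it runs from 0.45 to 0.40. Stopping the count at age 6 brings it to 0.77–0.79; the residue arises because the youngest children have not reached 6.

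**Step 6: precision cost of the remedy.** For a birth-date term, the standard-error multiplier against the unadjusted all-births contrast is 1/√(1 − R²), with R² from exposure on birth date. For later births only it is √[(1/nE + 1/nUc)/(1/nE + 1/nU)], with nE = (1 − p)u, nU = 1 − nE and nUc = (1 − p)(1 − u). Both are linear-model approximations before other covariates.

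| Uptake u | R², linear | Linear term | Cubic term | Later births only |
|---|---|---|---|---|
| 50% | 0.194 | 1.11 | 1.14 | 1.17 |
| 70% | 0.331 | 1.22 | 1.28 | 1.37 |
| 90% | 0.545 | 1.48 | 1.66 | 2.10 |
| 100% | 0.705 | 1.84 | 2.40 | not estimable |

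At 100% uptake an era indicator is perfectly collinear with exposure, and a smooth birth-date term separates the two only by extrapolation.

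**The case against.** The strongest reply is that the logistic model is unspecified, not restricted: birth date is nowhere excluded, and below full uptake the data would include concurrent untreated infants. That is correct. A reader might infer that the plan cannot separate probiotics from era; the documents support only that it does not commit to doing so. The missing covariate list is the wider gap. Birth era still deserves its own mention, because its link with exposure is fixed by the stated dates.

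A second reply is that every magnitude is assumed. This also stands. A trend of 5% per year compounds over 13 years to a 1.9-fold rise or roughly a halving, which nothing in the documents supports, and at 1% the shift is small.

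A third is that the only calendar trend described is a rise, which works against a protective finding. A reader might infer the reverse, that the association in the title is an artefact of era. The documents do not show that either. The general rise is not shown for this population, and the follow-up effect depends on how the outcome was counted, which is not stated.

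Finally, later untreated infants may be untreated because enteral feeding was slow to become satisfactory. Restricting to later births could then exchange era bias for selection by illness. This stands as a limit on the remedy, and the report should say so.

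**Conclusion.** The point holds as a cheap improvement. By the documents' own dates, 38% of the window supplies essentially only unexposed infants, and nothing planned is committed to distinguishing probiotic use from birth era in the probiotic-versus-none contrast. The net direction and size of any bias cannot be determined from the documents. The risk-ratio ranges (0.94 to 1.07 and 0.72 to 1.38) illustrate sensitivity and are not estimates; they rest on assumed uptake, trend, even births and no probiotic effect. Only the calendar split is documented. A common outcome age would address unequal follow-up but would leave any real change in risk between eras.

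**What to change.** 1. Tabulate probiotic uptake by birth year first; the plan says "probiotic administration and strain administered are recorded". State whether outcomes have already been seen, since the title already reports an association.
2. State that the probiotic-versus-none conclusion rests on a logistic model with birth date, gestational age, birth weight and first-degree family history, plus feeding status before probiotic eligibility if dated records exist. Treat the Chi-square as descriptive.
3. Repeat that model in births from December 2013 onward with the same covariates, so that a difference between the two results reflects the population and not the adjustment set. Birth date may be dropped here if concurrent controls are sparse. State that later untreated infants may differ, because the probiotic followed satisfactory enteral nutrition.
4. Count the outcome up to the same age in both eras where records allow; otherwise report the difference in follow-up as a limitation.
5. Fix the minimum number of concurrent unexposed infants before fitting. Below it, report a before-after (historical-control) association and do not attribute it to probiotics.

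The cost is SAP wording, one table and extra model runs on records the unit should already hold. The downside is wider intervals: standard errors about 1.1 to 1.8 times larger with a linear birth-date term at 50% to 100% uptake, and about 1.2 to 2.1 times for later births only at 50% to 90%. At 100% the later-births analysis cannot be done.

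### Probiotics started only after satisfactory enteral feeding, but the no-probiotic infants are not held to that condition, so the contrast can carry selection on feeding tolerance of unknown size and direction

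*Combined protocol and SAP*

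**What the plan says.** Under Design and Methods, the Nutritional management text gives the exposure rule: "The probiotic was introduced after initiation of satisfactory enteral nutrition and continued until 35 weeks postnatal or until discharge from the unit". It sets no volume, day or tolerance threshold for satisfactory. The same text dates the practice: "In our unit, the use of probiotics was initiated in December 2013 as a preventive measure against the development of necrotising enterocolitis".

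The cohort covers infants "hospitalised in the Neonatal Intensive Care Unit at the Hospital Universitario Clínico San Cecilio between January 2009 and December 2021". The Inclusion and exclusion criteria admit "All patients hospitalised in the Neonatal Intensive Care Unit with < 1500 grams birth weight and/or < 32 weeks at birth", and then: "Deceased patients, incomplete or unavailable medical history and patients with severe congenital diseases are excluded". No feeding milestone appears in either statement, and no comparator group is defined.

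Main objective 2 needs the probiotic contrast: "To assess whether the use of breastfeeding and probiotic supplementation in very low birth weight infants as prophylaxis for necrotising enterocolitis is associated with" less atopic dermatitis at preschool and school age. Secondary objective 1 asks whether breast milk and probiotics act synergistically.

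Statistical Considerations lists Mann-Whitney tests, Chi-square tests and a multivariate logistic regression. It names no covariates and describes no landmark, matching or restriction.

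**The concern.** An infant could be exposed only after passing a clinical condition. The comparator is every other included infant, whether or not the condition was reached. If some infants never reached it, or left the unit first, they can only be in the no-probiotic group.

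That matters because feeding tolerance is plausibly tied to maturity, illness, time on parenteral nutrition and type of milk. The Background supplies the link to outcome: it lists immaturity and limits on starting enteral feeding among the causes of disturbed gut colonisation, and says dysbiosis may precede atopic dermatitis. The start condition is thus related to exposure by rule and to outcome by the plan's own rationale. A difference between groups could appear with no probiotic effect at all. Secondary objective 1 shares the problem, because milk type may influence who reaches the condition.

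This is distinct from calendar time. It would remain if practice had been the same throughout 2009-2021, and adjusting for year of birth would not remove it.

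**Working it through.** The plan states no sample size, event rate or effect size, so there is no figure of its own to reproduce. The check has two parts.

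**1. Setting the texts side by side**

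| | Exposed | Not exposed |
|---|---|---|
| Birth weight and/or gestation limit | applies | applies |
| Exclusions (death, records, severe congenital disease) | apply | apply |
| Satisfactory enteral nutrition reached | required by the start rule | not required |
| Adjustment for feeding tolerance | not prespecified | not prespecified |

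The asymmetry follows from the wording alone. How many infants it affects does not.

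**2. How large the bias could be**

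From the documents:
- January 2009 to November 2013: 4 × 12 + 11 = 59 months.
- December 2013 to December 2021: 156 − 59 = 97 months.
- So 59/156 = 37.8% of admission months precede probiotic use.

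Assumed, because the documents give none of these:
- admissions are even over the 156 months;
- a fraction f of included infants never meets the condition, the same in both periods;
- every infant who meets it in the later period is treated;
- dermatitis risk is 20% in infants who met it, and 30% or 10% in those who did not;
- the probiotic has no effect.

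Formulas:
- Share of the unexposed who never met the condition: s = 156f / (59 + 97f).
- Unexposed risk: p = 0.20(1 − s) + r·s, with r = 0.30 or 0.10.
- Spurious odds ratio: (0.20/0.80) / (p/(1 − p)).

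| f | s | p if r = 30% | OR | p if r = 10% | OR |
|---|---|---|---|---|---|
| 1% | 1.56/59.97 = 2.6% | 20.3% | 0.98 | 19.7% | 1.02 |
| 2% | 3.12/60.94 = 5.1% | 20.5% | 0.97 | 19.5% | 1.03 |
| 5% | 7.80/63.85 = 12.2% | 21.2% | 0.93 | 18.8% | 1.08 |
| 15% | 23.40/73.55 = 31.8% | 23.2% | 0.83 | 16.8% | 1.24 |

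A second calculation sets the share directly and uses a risk ratio, with baseline risk 10-20%. If the risk ratio is 2, the odds ratio is 0.94-0.95 when 5% of the unexposed never met the condition, and 0.71-0.74 when 30% did not. If it is 0.5, the 30% case gives 1.20-1.22. If the risk ratio is 1, there is no bias.

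**The case against.** The strongest reply is that the rule describes timing and is not a hurdle that many infants fail. Deaths and severe congenital disease are excluded, and these are probably the infants least likely to establish feeds. The condition requires only that satisfactory feeding has begun. Survivors may nearly all reach it. This stands as a limit on size: at 1-2% the bias is trivial. It does not remove the point, because the documents report no share and the plan therefore cannot show that the bias is negligible.

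A second reply is that logistic regression could adjust. With no covariates named, nothing commits the analysis to that. Naming gestational age, birth weight and feeding variables would deal with much of the problem, but not where untreated infants have few treated counterparts with similar feeding histories.

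A reader might infer that untreated infants born from December 2013 are mostly those who failed the condition, so that the bias is greatest there. With the same assumed risks, a comparison confined to those births, in which 50-100% of the unexposed never met the condition, gives odds ratios of 0.75-0.58 or 1.42-2.25. The documents do not support that reading. They say probiotic use began in that month, not that nearly all infants then received it; gradual uptake or clinician choice would also leave infants untreated. Nor does the plan propose a comparison confined to later births, so those figures do not measure bias in the planned contrast.

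**Conclusion.** The point holds as a risk of selection bias that the plan leaves open. By its own rule the exposed infants had established feeds, while the unexposed are unrestricted. This affects main objective 2 and secondary objective 1. It does not affect a comparison of strains among treated infants.

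Size and direction are unknown. The illustrated odds ratios run from about 0.97-1.03 (1-2% never meeting the condition) to 0.93-0.83 or 1.08-1.24 (5-15%), and they rest wholly on the assumed risks, even admissions and full treatment of eligible later infants. How many infants from December 2013 went untreated because of feeding is not documented. It would also be too strong to say that any observed probiotic association is produced by this selection; the documents show only that the planned analysis could not rule it out. The change should be made because it is cheap and the plan offers no other protection.

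**What to change.** In the protocol and SAP:

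1. Define the no-probiotic group. For analysis purposes only, turn the start condition into one rule that can be read from the recorded enteral data, and find the day each infant in both periods first met it.
2. Restrict the probiotic-versus-none comparison to infants who met it before the earlier of the documents' 35-week stop and discharge. Discharge alone is not enough, since an infant meeting the condition after the 35-week stop could not have been treated under the stated rule.
3. Adjust for gestational age, birth weight and the day the condition was met.
4. Report infants who never met it separately, and show the unrestricted analysis alongside.
5. Tabulate exposure by admission period within the restricted set, and include admission period in the model where overlap allows. Where nearly all later infants who met the condition were treated, state that the contrast is before versus after December 2013 and cannot be separated from calendar time.

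The cost is wording and a derived variable; no care changes. Some infants leave the comparison, and few concurrent controls may remain. The protocol says enteral data are recorded and daily intakes calculated, but not that daily enteral volumes are in the dataset. If they are not, the date of first established enteral feeding must be taken from the existing records, which is more work.
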